### Classification of an AE (Severity of Event)

For adverse events (AEs), guidelines will be used to describe severity.

- **Mild** – Events require minimal or no treatment and do not interfere with the participant's daily activities.
- **Moderate** – Events result in a low level of inconvenience or concern with the therapeutic measures. Moderate events may cause some interference with functioning.
- **Severe** – Events interrupt a participant's usual daily activity and may require systemic drug therapy or other treatment. Severe events are usually potentially life-threatening or incapacitating. Of note, the term "severe" does not necessarily equate to "serious".

### Classification of an AE (Relationship to Study Intervention)

All adverse events (AEs) will be assessed for relationship to study intervention as the following:

**Definitely Related** – There is clear evidence to suggest a causal relationship, and other possible contributing factors can be ruled out. The clinical event, including an abnormal laboratory test result, occurs in a plausible time relationship to taking voxelotor and cannot be explained by concurrent disease or other drugs or chemicals. The response to withdrawal of the study intervention (dechallenge) should be clinically plausible. The event must be pharmacologically or phenomenologically definitive, with use of a satisfactory rechallenge procedure if necessary.

**Probably Related** – There is evidence to suggest a causal relationship, and the influence of other factors is unlikely. The clinical event, including an abnormal

laboratory test result, occurs within a reasonable time after taking voxelotor, is unlikely to be attributed to concurrent disease or other drugs or chemicals, and follows a clinically reasonable response on withdrawal (dechallenge). Rechallenge information is not required to fulfill this definition.

**Potentially Related** – There is some evidence to suggest a causal relationship (e.g., the event occurred within a reasonable time after taking voxelotor). However, other factors may have contributed to the event (e.g., the participant's clinical condition, other concomitant events). Although an AE may rate only as "possibly related" soon after discovery, it can be flagged as requiring more information and later be upgraded to "probably related" or "definitely related", as appropriate.

**Unlikely to be related** – A clinical event, including an abnormal laboratory test result, whose temporal relationship to voxelotor makes a causal relationship improbable (e.g., the event did not occur within a reasonable time after taking voxelotor) and in which other drugs or chemicals or underlying disease provides plausible explanations (e.g., the participant's clinical condition, other concomitant treatments).

**Not Related** – The AE is completely independent of voxelotor, and/or evidence exists that the event is definitely related to another etiology. There must be an alternative, definitive etiology documented by the clinician.

**Classification of an AE (Expectedness)** \*additional information can be found in Attachment A at the end of this document

The PI will be responsible for determining whether an adverse event (AE) is expected or unexpected. An AE will be considered unexpected if the nature, severity, or frequency of the event is not consistent with the risk information previously described for the study intervention.

Expected AEs include the following: headache, diarrhea, abdominal pain, nausea, fatigue, rash, and pyrexia.

### **5.5 Time Period and Frequency for Event Assessment and Follow-up**

The occurrence of an adverse event (AE) or serious adverse event (SAE) may come to the attention of study personnel during study visits and interviews of a study participant presenting for medical care, or upon review by the study PI.

All AEs including local and systemic reactions not meeting the criteria for SAEs will be captured on the appropriate study database form. Information to be collected includes event description, time of onset, clinician's assessment of severity, relationship to study product (assessed only by those with the training and authority to make a diagnosis), and time of resolution/stabilization of the event. All AEs occurring while on study must be documented appropriately regardless of relationship. All AEs will be followed to adequate resolution.

Any medical condition that is present at the time that the participant is screened will be considered as baseline and not reported as an AE. However, if the study participant's condition deteriorates at any time during the study, it will be recorded as an AE.

Changes in the severity of an AE will be documented to allow an assessment of the duration of the event at each level of severity to be performed. AEs characterized as intermittent require documentation of onset and duration of each episode.

The PI or study coordinator will record all reportable events with start dates occurring any time after informed consent is obtained until 7 (for non-serious AEs) or 30 days (for SAEs) after the last day of study participation. At each study visit, the investigator will inquire about the occurrence of AE/SAEs since the last visit. Events will be followed for outcome information until resolution or stabilization.

### **5.6 Adverse Event Reporting**

AEs will be reported to Pfizer at regular intervals as required by Pfizer. SAEs will be reported to Pfizer within 24 hours after the investigator learns of the event and to the IRB according to IRB Policies & Procedures. The Sponsor-Investigator will be responsible for notifying the FDA of any unexpected fatal or life-threatening suspected SAE as soon as possible, but in no case later than 7 calendar days after Sponsor-Investigator's initial receipt of the information.

Expected AEs will be recorded in CRFs.

### **5.7 Serious Adverse Event Reporting**

The study principal investigator will immediately report to Emory IRB according to their Policies & Procedures as well as to Pfizer any serious adverse event, whether or not considered study intervention related, including those listed in the protocol or investigator brochure and must include an assessment of whether there is a reasonable possibility that the study intervention caused the event within 24 hours of finding out about the event. Study endpoints that are serious adverse events (e.g., all-cause mortality) must be reported in accordance with the protocol unless there is evidence suggesting a causal relationship between the study intervention and the event (e.g., death from anaphylaxis). In that case, the investigator must immediately report the event to the IRB and Pfizer.

All serious adverse events (SAEs) will be followed until satisfactory resolution or until the PI deems the event to be chronic or the participant is stable. Other supporting documentation of the event may be requested by Pfizer and should be provided as soon as possible.

The Sponsor-Investigator will be responsible for notifying the Food and Drug Administration (FDA) of any unexpected fatal or life-threatening suspected adverse reaction as soon as possible, but in no case later than 7 calendar days after the initial receipt of the information from the study principal investigator. The Sponsor-Investigator or Designee must notify the FDA and all participating investigators in an Investigational New Drug (IND) safety report of potential serious

risks, from clinical trials or any other source, as soon as possible, but in no case later than 15 calendar days after the Sponsor-Investigator determines that the information qualifies for reporting. In addition, the Sponsor-Investigator is responsible for notifying Pfizer of the FDA reported safety event and provide all documentation submitted to the FDA, including the safety event narrative.

### **5.8 Reporting of Pregnancy**

In the event of pregnancy that occurs during study, the pregnancy will be reported to GBT Pharmacovigilance or Designee and the decision for the participant to continue on study or not will depend on the specific situation and will be discussed with GBT Pharmacovigilance or Designee. Pregnancies should be monitored for the full duration of pregnancy and/or followed through to a definitive outcome. The outcome of a pregnancy event will be reported to GBT Pharmacovigilance or Designee.

### **5.9 Unanticipated Problems**

#### **Definition of Unanticipated Problems (UP)**

The Office for Human Research Protections (OHRP) considers unanticipated problems involving risks to participants or others to include, in general, any incident, experience, or outcome that meets all of the following criteria:

- Unexpected in terms of nature, severity, or frequency given (a) the research procedures that are described in the protocol-related documents, such as the Institutional Review Board (IRB)-approved research protocol and informed consent document; and (b) the characteristics of the participant population being studied;
- Related or possibly related to participation in the research (“possibly related” means there is a reasonable possibility that the incident, experience, or outcome may have been caused by the procedures involved in the research); and
- Suggests that the research places participants or others at a greater risk of harm (including physical, psychological, economic, or social harm) than was previously known or recognized.

This definition could include an unanticipated adverse device effect, any serious adverse effect on health or safety or any life-threatening problem or death caused by, or associated with, a device, if that effect, problem, or death was not previously identified in nature, severity, or degree of incidence in the investigational plan or application (including a supplementary plan or application), or any other unanticipated serious problem associated with a device that relates to the rights, safety, or welfare of subjects (21 CFR 812.3(s)).

#### **Unanticipated Problems Reporting**

The investigator will report unanticipated problems (UPs) to the reviewing Institutional Review Board (IRB) and to the principal investigator (PI). The UP report will include the following information:

- Protocol identifying information: protocol title and number, PI's name, and the IRB project number;
- A detailed description of the event, incident, experience, or outcome;
- An explanation of the basis for determining that the event, incident, experience, or outcome represents an UP;
- A description of any changes to the protocol or other corrective actions that have been taken or are proposed in response to the UP.

To satisfy the requirement for prompt reporting, UPs will be reported using the following timeline:

- UPs that are serious adverse events (SAEs) will be reported to the IRB and to GBT Pharmacovigilance or Designee within 24 hours of the investigator becoming aware of the event.
- Any other UP will be reported to the IRB and to GBT Pharmacovigilance or Designee within 10 days of the investigator becoming aware of the problem.
- All UPs should be reported to appropriate institutional officials (as required by an institution's written reporting procedures), the supporting agency head (or designee), and the Office for Human Research Protections (OHRP) within 10 days of the IRB's receipt of the report of the problem from the investigator.

### **5.10 End of Study**

A participant is considered to have completed the study if he or she has completed all phases of the study including the last visit or the last scheduled procedure shown in the Schedule of Activities (SoA). For patients continuing commercial Voxelotor after 12w, the end of treatment (12w) visit will also serve as the end of study visit. Patients who will not continue commercial Voxelotor after 12w will complete an end of study visit up to 8 weeks after last study dose.

### **6. Data and Specimen Banking**

Data obtained during this research may be stored for future use. Data will be stored indefinitely on password protected computers on servers managed by Children's Healthcare of Atlanta/Emory University and only accessible by authorized personnel. Paper data is stored in a locked cabinet in a locked office. Only study personnel have access to input data into electronic database. Data collected and stored will include, but not limited to:

- demographic data
- data collected from surveys
- medical treatment data

Data will be maintained for the duration of the study and thereafter as required by funding sources.

Deidentified data from this study may be requested from other researchers after the completion of the primary endpoint by contacting the Principal Investigator and presenting appropriate regulatory approvals.

No biological specimens will be retained, and no genetic material will be collected in this study.

## **7. Sharing of Results with Participants**

In the event that medically significant and clinically actionable results are found, this information will be shared with providers. Results would be provided to the subject's physician who will discuss with the patient or legal guardian and appropriate treatment, repeat testing, genetic counseling or follow-up testing would be discussed and decided locally on a case by-case basis.

## **8. Study Timelines**

The duration of an individual participant's participation in the study is approximately 16 weeks. We anticipated enrolling about 5-8 subjects per month, with 9 month expected duration to enroll all study participants. The estimated date for the investigators to complete this study is 28 months.

## **9. Inclusion and Exclusion Criteria**

### **9.1 Inclusion Criteria**

Subjects will be recruited from the CHOA Aflac Sickle Cell Comprehensive Clinics located at the Scottish Rite campus and the Egleston campus.

In order to be eligible to participate in this study, an individual must meet all of the following criteria:

1. Written informed parental/guardian consent and participant assent for patients < 18y or written informed consent for patients > 18y has been obtained per institutional review board (IRB)/Ethics Committee (EC) policy and requirements, consistent with ICH guidelines.
2. Stated willingness to comply with all study procedures and availability for the duration of the study
3. Male or female participants, ages 4 to 30 years, inclusive
4. Homozygous hemoglobin SS (HbSS) or hemoglobin S/beta thalassemia (HbS/β thal
5. Hemoglobin (Hb): Hb ≤10.5 g/dL at baseline
6. Concomitant hydroxyurea (HU) therapy is allowed if the dose has been stable for at least 3 months with no anticipated need for dose adjustments during the study and no sign of hematological toxicity.
7. Ability to take oral medication and willingness to adhere to daily voxelotor and scheduled DCS/NIRS assessments.

8. If sexually active and female, must agree to abstain from sexual intercourse or to use a highly effective method of contraception throughout the study period and for 30 days after discontinuation of study drug. If sexually active and male, must agree to abstain from sexual intercourse or willing to use barrier methods of contraception throughout the study period and for 30 days after discontinuation of study drug.
9. Females of child-bearing potential, i.e., who have begun menstruation and are sexually active, are required to have a negative pregnancy test at screening before the initial administration of study drug.

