## 5.2 Schedule of Assessments (SoA)

FDNIRS/DCS and TCD measurements will be made on D1, or within the screening period depending on researcher availability. For the 4w, 8w, and 12w and end of study visits, the time point given spans a window of +/- 7 days. For patients continuing commercial voxelotor after 12w, the end of treatment (12w) visit will also serve as the end of study visit. Patients who will not continue commercial voxelotor after 12w will complete an end of study visit up to 8 weeks after last study dose.

	Screening (up to 28 days)	Treatment				End of Study (up to 8 wks post-treatment)
		D1 (+/- 7d)	4w (+/- 7d)	8w (+/- 7d)	12w (+/- 7d)	
Consent/Accent	X					
Inclusion/Exclusion Criteria	X					
Medical History & PE	X	X			X	
Height, weight	X				X	X
Vital signs, pulse oximetry	X	X	X	X	X	X
CBC diff, retic	X	X	X	X	X	X
CMP & LDH	X				X	X
Hb Electrophoresis	X				X	
Hb morphology	X	X	X	X	X	X
RBC Health		X			X	
FDNIRS/DCS (performed by [name] Lab staff)		X	X		X	
Transcranial Doppler ultrasound (TCD)	(X)	X			X	
Pregnancy testing (for females of child bearing potential)	X					
Adverse event reporting	X	X	X	X	X	X
Drug dispensing		X	X	X	X	

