## 5.3 Efficacy, Safety, and Other Assessments

Screening will occur up to 28 days prior to the start of the study. The subject's medical chart will be used for screening and for part of collection of trial data, per Health Insurance Portability and Accountability Act (HIPAA) rules, other relevant federal or state laws, and local institutional requirements, as applicable. Information obtained from the medical chart will include:

- a) List of current medications and their doses
- b) Vital signs

- c) Transfusion history
- d) Stroke history
- e) Previous MRI and/or MRA's
- f) Previous sleep studies
- g) Previous transcranial Doppler ultrasound results.

The study procedures and evaluations to be done as part of the study to support the determination of efficacy, as per the primary and secondary objectives outlined in this protocol, will include:

- **DCS/FDNIRS assessments.** Measurements of cerebral blood flow, oxygen extraction, and oxygen metabolism will be made by a trained study staff personnel using a customized diffuse correlation spectroscopy combined with frequency domain near infrared spectroscopy oximeter (Figure 2). A DCS/FDNIRS optical sensor will be manually held over the right and left forehead to obtain a brief (<1min) resting state measure of brain hemodynamics.

Measurements will be repeated up to 3 times per hemisphere (Figure 3). Total time of exam is typically 15-30 minutes. Measurements will be made before, and at 4 and 12 weeks after the start of voxelotor. Measurements will be obtained in quiet area of Aflac outpatient clinics using PPE and hand hygiene practices according to hospital policy.

- A research blood specimen will be obtained when a clinical sample is unavailable. Up to sixteen mLs of venous blood will be collected at each visit. Laboratory assessments relevant to measures predictive of voxelotor response and to measures of RBC Health will be performed at local (central CHOA lab) clinical labs. Local laboratory assessments will include complete blood count, reticulocyte count, hemoglobin electrophoresis, RBC dense cells and measures of RBC hemolysis (LDH, indirect bilirubin). RBC health laboratory assessments will include but are not limited to RBC adhesion.
- **Procedures that will be completed during the study as part of regular standard of clinical care:** These include physical examination, vital sign assessment (heart rate, blood pressure, pulse oximetry, etc.), medical history.

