15. Pregnant patients
16. Evidence of abnormal high blood flow velocities on TCD of 200 cm/sec or more

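### The only scheduled pregnancy test is at Screening, up to 28 days before first dose, and nothing scheduled confirms the pregnancy exclusion when study drug is first dispensed

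*Combined protocol and SAP*

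**What the plan says.** Section 9.2, criterion 15, makes "Pregnant patients" ineligible. Section 9.1, criterion 9, says how this is checked: females who have begun menstruation and are sexually active "are required to have a negative pregnancy test at screening before the initial administration of study drug". It fixes the order of test and dose but gives no maximum interval between them.

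In section 5.2, the row "Pregnancy testing (for females of child bearing potential") carries a single mark, under Screening. The inclusion/exclusion row is likewise marked only at Screening. Drug dispensing is marked at D1, 4w, 8w and 12w.

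On timing, section 5.3 states: "Screening will occur up to 28 days prior to the start of the study". The table header agrees: "Screening (up to 28 days"). The table also heads the D1 column with a window of plus or minus 7 days, whereas the text above it says: "For the 4w, 8w, and 12w and end of study visits, the time point given spans a window of +/- 7 days". D1 is not in that list.

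Criterion 8 requires that sexually active females "must agree to abstain from sexual intercourse or to use a highly effective method of contraception throughout the study period" and for 30 days after stopping drug. The protocol does not define when the study period begins.

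**The concern.** The plan treats pregnancy on study drug as a serious matter. It is an exclusion (section 9.2), a listed reason for withdrawal (section 13.2), and an event to be reported and followed to outcome (section 5.8). Attachment A makes exposure during pregnancy reportable separately from any associated serious adverse event. All of these provisions depend on a pregnancy being recognised, yet the only scheduled step aimed at recognising one may be four weeks old when dosing begins.

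Criterion 9 confines the test to females who are already sexually active. That is the group whose status can change between test and dose, or in whom a conception shortly before consent may be too early to show at Screening. Enrolment runs to age 30, so the group is unlikely to be empty, although its size is not given. What is at stake is unrecognised exposure at first dose in a participant whom the protocol meant to exclude.

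**Working it through.** The plan states no test-to-dose interval to reproduce. The check is arithmetic on visit windows, followed by a reading of the schedule.

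**Inputs**
- Screening window: 28 days (section 5.2 table header; section 5.3 text).
- D1 window: 7 days either side (section 5.2 table header only).
- Treatment: 12 weeks (Study Summary; section 5.2) = 12 × 7 = 84 days.
- Individual duration: up to 16 weeks (Study Summary) = 16 × 7 = 112 days.

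**Longest interval from test to first dose**
- D1 within the 28-day screening limit: 28 days.
- D1 header window added on its late side: 28 + 7 = 35 days.

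**Which figure is supported**
- Both the header and section 5.3 give 28 days.
- 35 days rests on the D1 header alone. The text above the table gives windows for 4w, 8w, 12w and end of study, but not for D1.
- 28 + 84 = 112 days equals the stated 16 weeks, whereas 35 + 84 = 119 days exceeds it. This supports 28 days only modestly. The end-of-study visit for those not continuing commercial drug may come up to 8 weeks after the last dose, and 12 + 8 = 20 weeks does not fit within 16 weeks on either reading.

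So 28 days is the secure maximum and 35 an upper reading. Both are maxima: a Screening test done close to D1 also complies.

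**What is marked at each point (section 5.2)**

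| | Screening | D1 | 4w | 8w | 12w | End of study |
|---|---|---|---|---|---|---|
| Pregnancy test | X | | | | | |
| Eligibility check | X | | | | | |
| Drug dispensing | | X | X | X | X | |

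The table was flattened when the text was extracted, but a single mark in the Screening position agrees with criterion 9.

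**Consequence**
1. A participant tests negative at Screening, up to 28 days before D1. Criterion 9 is met.
2. She conceives after the test, or shortly before it and too early to detect.
3. At D1 neither the pregnancy row nor the eligibility row applies, and drug is dispensed.
4. Criterion 15 is breached at first dose without any scheduled test showing it.

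**The case against.** The strongest reply is that the plan is consistent with itself. Criterion 9 calls for a test at Screening, the schedule places it there, eligibility is checked there, and the monitoring table in section 18 has eligibility confirmed at enrolment. On that view a Screening test is simply the chosen way to apply criterion 15. This stands in part: criterion 9 and the schedule do agree, and a reader who inferred a contradiction between them would be wrong. The gap lies between those two and criterion 15, whose status at first dose nothing confirms.

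A second reply is that criterion 8 covers the interval. If the study period starts at consent, sexually active females have agreed to abstinence or highly effective contraception from then on. That lowers the risk. It remains an agreement and not a verification, it cannot cover conception just before consent, and the start of the study period is undefined.

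Third, a reader might infer that no later visit could reveal a pregnancy. The documents do not support that. History and examination recur at D1 and 12w, and section 5.5 has the investigator ask about adverse events at each visit. What can be said is that no later test is scheduled.

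Fourth, the harm is not quantified. Section 14 describes no reproductive risk, section 13.2 lets the investigator decide on withdrawal, and section 5.8 leaves continuation to the specific situation. This limits how strongly the point can be put, but it does not remove a stated exclusion that goes unverified at first dose.

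**Conclusion.** The point holds in this form: one scheduled test, at Screening, up to 28 days before first dose, with neither the test nor the eligibility check repeated when drug is first dispensed. A participant can comply with criterion 9 and be pregnant at first dose despite criterion 15. This is a gap in verifying a safety rule that the plan itself sets, and it deserves correction.

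A reader might take 35 days as the gap, or 119 days as the time from test to the end of dosing. Both need the D1 header window to extend the screening limit, which the text above the table and section 5.3 do not support. A reader might also infer that the Screening test ought to be replaced by one at D1. The documents do not settle that. It is a clinical-management choice with its own drawback, because a pregnancy would then come to light only after screening procedures had been done.

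The conclusion assumes that the schedule lists every required test. The share of participants concerned depends on how many sexually active females enrol, which the documents do not give.

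**What to change.** Reconcile criterion 9, the pregnancy-testing row of the schedule and criterion 15, so that the pregnancy exclusion is verified as current when study drug is first dispensed. Reconcile the 7-day window in the D1 header with the text above the table, so that the longest interval from Screening to first dose is unambiguous. It would also help to state when the study period in criterion 8 begins. The timing of the test, and whether to repeat it, are for the sponsor-investigator to set.

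The cost is small. D1 is already a visit with history, examination and blood work, so no extra visit is implied. An occasional exclusion may be found at D1 rather than at Screening. The change needs a short amendment with IRB approval, as the Statement of Compliance requires.
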